10.4 Events Requiring Immediate Reporting

10.4.1 Serious Adverse Events and Non-Serious ≥ Grade 3 Adverse Events

SAEs and non-serious \geq grade 3 AEs must be reported from the investigational site to the sponsor no later than 24 hours following a) the patient visit at which such AE was reported, noted or recognized; or b) the principal investigator's or any investigator personnel's receipt of the test results or other information at, or from which, such development was reported, noted or recognized.

Grade 3 and 4 abnormal laboratory test results must be reported as AEs when these are assessed as clinically significant by the reporting investigator.

All events fulfilling the definition of Hy's Law (i.e. $ALT/AST > 3 \times ULN$ and Bilirubin $> 2 \times ULN$) must be reported as SAEs.

10.4.2 Overdose and Medication Errors

For this trial, an overdose is defined as a patient receiving a dose of the IMP 10% in excess of the intended dose specified in this protocol.

Decisions regarding dose interruptions or modifications will be made by the investigator in consultation with the Medical Monitor based on the clinical evaluation of the patient.

Medication errors include infusion rate errors and uses outside what is foreseen in the protocol, including misuse and abuse of the product.

All events of overdose and/or medication errors with IMP must be reported from the investigational site to the sponsor within 24 hours of awareness whether associated with an adverse event or not.

In addition, overdose and/or medication errors with IMP must also be recorded in the AE page of the eCRF whether associated with an AE or not.

Overdose, medication errors, misuse and abuse do not automatically make an AE serious, but if the consequences are serious, for example death or hospitalizations, the event is serious and must be reported as an SAE.

Rescue medication to reverse the action of GEN1029 is not available. In case of overdose, medication errors, misuse and/or abuse of trial drug patients should receive supportive care according to local guidelines and potential side effects of GEN1029 should be treated symptomatically.

In the event of an overdose, the investigator should:

- i. Contact the Medical Monitor immediately.
- ii. Closely monitor the patient for any AE/SAE and laboratory abnormalities until GEN1029 can no longer be detected systemically.
- iii. Obtain a plasma sample for PK analysis if requested by the Medical Monitor (determined on a case-by-case basis).
- iv. Document the quantity of the excess dose as well as the duration of the overdose in the CRF.

10.4.3 Pregnancy

Any pregnancy that occurs during trial participation must be reported. Pregnant trial patients must be withdrawn from treatment immediately, whereas male patients may continue in the trial should pregnancy of female partners occur. In this case, a separate informed consent will be obtained from the female partner for collection of information regarding the pregnancy.

Each pregnancy must be reported to sponsor or designee within 24 hours of learning of its occurrence. The pregnancy must be followed-up to determine outcome (including premature termination) and status of mother and child. The child must be followed at least to the age of one month. Pregnancy complications and elective terminations for medical reasons must be reported as an AE or SAE. Spontaneous abortions must be reported as an SAE. Any SAE occurring in association with a pregnancy brought to the investigator's attention after the patient has completed the trial and considered by the investigator as possibly related to the IMP, must be promptly reported to sponsor or designee.

10.4.4 Timelines for Immediate Reporting

The required timeframes and reporting forms for reporting of serious adverse events (SAEs), non-serious \geq grade 3 adverse events (NS \geq grade 3 AEs), overdose, medication errors and pregnancies are presented in Table 10-1.

Table 10-1 Timeframes for Reporting SAEs, NS≥Grade 3 AEs, Overdose, Medication errors and Pregnancies

		Initial Reports	Follow-up Information on a Previous Report			
Type of Event Time Frame		Documents	Time Frame	Documents		
All SAEs and NS \geq	24 hours*	Safety Reporting Form	24 hours*	Site DCF		
grade 3 AEs***			3 days **	CDS DCF		
All events of Overdose	24 hours*	Safety Reporting Form	24 hours*	Site DCF		
and/or Medication errors with IMP			3 days **	CDS DCF		
Pregnancy	24 hours*	Pregnancy Form	3 days	Updated Pregnancy Form		

DCF=Data Clarification Form; CDS=Corporate Drug Safety

* All new information regarding SAEs (initial and follow-up) must be reported from sites to sponsor within 24 hours.
 ** Sites should make every effort to respond to follow-up queries from sponsor within 3 business days if information is available.

*** AESIs that are serious or NS \geq grade 3 AEs should follow these reporting timelines.

Completed Safety Reporting Forms, Pregnancy Forms, DCFs or any IMP related SAE occurring any time after the patient has terminated trial participation, must immediately be forwarded to the Safety CRO:

If you have access to a secured email you may forward completed forms to

Email to:

If you do not have access to a secured email, please forward completed forms to

Fax: Europe: , US:

10.5 Suspected Unexpected Serious Adverse Reactions (SUSARs)

The sponsor has a legal responsibility to notify, as appropriate and according to local regulations, both the local regulatory authority and other regulatory agencies about the safety of the product under clinical investigation. Prompt notification of SAEs by the investigator to the sponsor is essential so that legal obligations and ethical responsibilities towards the safety of patients are met.

The sponsor will ensure that all relevant information about Suspected Unexpected Serious Adverse Reactions (SUSARs) is recorded and reported as soon as possible, but within a maximum of 15 calendar days (fatal or life-threatening SUSARs within a maximum of seven days) of first knowledge by the sponsor or designee, to the competent regulatory authorities and/or to the ethics committee according to the applicable local regulatory requirements. Relevant follow–up information of fatal or life-threatening SUSARs will be communicated subsequently within an additional eight days.

The investigator should be aware of local reporting regulations to the IEC/IRB. The safety CRO will either supply the investigator with the reports which should be passed on to the IEC/IRB or report directly to the IEC/IRB, depending on local regulations.

10.6 Follow-Up on Adverse Events

All AEs should be followed until they are resolved or until the safety follow-up visit, whichever comes first. At least possibly related non-serious \geq grade 3 AEs and SAEs still ongoing after end of trial should be followed on a regular basis, according to the investigator's clinical judgment, until the event has been resolved or until the investigator assesses it as chronic and all queries have been resolved.

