8.3 Safety Follow up Evaluations

Patients discontinuing from treatment for any reason will have safety follow-up visits 30 and 70 days after last treatment and will also be contacted every 13 weeks after last dose until end of trial.

Data collected should be added to the adverse events eCRF and the concomitant medications eCRF.

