10.2 Adverse Event Reporting

Non-serious Adverse Events:

Non-serious AEs should be reported from the time the patient signs the ICF until the safety follow up visit (at 70 days after the last IMP dose) or the end of trial (EOT)/withdrawal visit), whichever comes first.

Serious Adverse Events

SAEs should be reported from the time the patient signs the ICF until the safety follow up visit (at 70 days after the last IMP dose) or the end of trial (EOT)/withdrawal visit, whichever comes first.

Please note:

- Final assessment of AEs must be performed by a medically qualified person, i.e., a medical doctor.
- All AEs that occur in patients during the AE reporting period must be reported, whether or not the event is treatment-related.
- All AEs should be entered in the eCRF and assessment should be made at each visit (or more frequently, if necessary) of changes in severity, the suspected relationship to the trial treatment, action taken to trial drug, and the outcome. Instructions for reporting changes in an ongoing AE during a patient's participation in the trial are provided in the eCRF completion guideline.
- If an AE becomes grade 3 or results in an SAE it should be reported both in the eCRF and on the relevant paper form (SAE paper form or non-serious grade 3 form).
- All AEs should be followed until they are resolved or until end of trial, whichever comes first. At least possibly related non-serious ≥ grade 3 AEs and SAEs still ongoing after end of trial should be followed on a regular basis, according to the investigator's clinical judgment, until the event has been resolved or until the investigator assesses it as chronic and all queries have been resolved.

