10.2.6 Laboratory test abnormalities

Laboratory abnormalities that are considered clinically significant, i.e. induce clinical signs or symptoms, require concomitant therapy or require changes in trial treatment should be recorded as an AE in the eCRF. Whenever possible, a diagnosis, rather than a symptom should be provided (e.g. anemia instead of low hemoglobin). Laboratory abnormalities that meet the criteria for AEs should be followed until they have returned to normal or an adequate explanation of the abnormality is found. When an abnormal laboratory or test result corresponds to a sign/symptom of an already reported AE, it is not necessary to separately record the laboratory/test result as an additional event.

NOTE: A CTCAE grade 3 or 4 event (severe) does not automatically indicate an SAE.

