In addition, time to onset of first AESI event (for subjects with at least one event), total number of AESI events, total number and percentage of AESI events with outcome of resolution, and time to resolution of each AESI event (for events which are resolved) will be summarized by AESI category using descriptive statistics. AESI events with partial start date will be imputed accordingly to the rules described in section 4.7. The same outputs will be created for the other event of interest: Pyrexia.

Time to onset of first AESI event will also be presented graphically by AESI category using Kaplan-Meier curves (one plot for each AESI category); in these Kaplan-Meier curves, subjects with no AESI will be censored at the end of the treatment period. Time to onset of first other event of interest: Pyrexia, using Kaplan-Meier curves will also be displayed.

AESI will also be presented graphically using swim lane plots. Plots will be performed individually for each subject, by dose level, and will show the reported AESI by category on a time-based x-axis (arrow will be used to show ongoing AEs). Plots will also include lines to show start date in the study (i.e., informed consent date) and last contact date of subject, as well as start and end dates of on-treatment period. Other event of interest: Pyrexia, will also be displayed on those swim lane plots.

Listings of all adverse events (including those from the pre and post-treatment periods) will be provided including the screening number/patient number (including site and country), age, race, sex, regimen, dose level, tumor type, verbatim, PT, SOC, duration of the event, highest severity, action taken, outcome, causality, date of onset, cycle of onset, date of resolution, days since the first dose, days since the latest dose, serious (Y/N), DLT (Y/N), infusion reaction (Y/N) and the treatment-emergent flag. AEs collected during the pre-treatment and post-treatment period will be flagged. Similar listings will also be created for each adverse events of interest separately.

Adverse Event will also be presented in a table by ADA status as applicable.

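### Protocol 10.2 and 10.6 stop the follow-up of ongoing AEs at different points, so the AESI resolution summaries for lower-grade and unrelated non-serious events can depend on which rule a site applies

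*Protocol*

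**What the plan says.** Two protocol sections set a general end to the follow-up of AEs already reported.

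- Section 10.2 (Adverse Event Reporting): "All AEs should be followed until they are resolved or until end of trial, whichever comes first".
- Section 10.6 (Follow-Up on Adverse Events): "All AEs should be followed until they are resolved or until the safety follow-up visit, whichever comes first".

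Both then make the same exception for at least possibly related non-serious AEs of grade 3 or higher and for SAEs. In 10.6 it reads in part: "SAEs still ongoing after end of trial should be followed on a regular basis, according to the investigator's clinical judgment".

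Section 10.2.6 covers laboratory abnormalities that qualify as AEs, which "should be followed until they have returned to normal or an adequate explanation of the abnormality is found". It gives no date and no link to the general rule.

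Section 10.6 does not name the visit by day. Section 8.3 provides "safety follow-up visits 30 and 70 days after last treatment", then contact every 13 weeks until end of trial.

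On the analysis side, SAP 17.3 will summarise, by AESI category, "total number and percentage of AESI events with outcome of resolution, and time to resolution of each AESI event", the latter for resolved events only.

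**The concern.** The two general rules cover the same events and end at different times, and no section says which prevails. Suppose an AE is still open at the safety follow-up visit. A site working from 10.6 can stop there and leave the outcome as not resolved. A site working from 10.2 keeps following and may later record a resolution date. The same clinical course then enters the database in two ways.

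The affected outputs are descriptive but they matter. Transaminase elevation and diarrhea are the two protocol-defined AESIs, and the SAP 17.3 summaries are where their reversibility will be read. Section 6.4.1 reports grade 2 or higher transaminase elevation in 14 of 27 patients, and section 10.3.2 reports diarrhea in more than 40%. The documents do not say how many of these events fall in the affected class.

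**Working it through.** The documents state no figure on this point, so there is none to reproduce. The check compares the passages and adds an illustration.

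**1. Do the two end-points coincide for a patient?** In general they do not.
- Table 1-1 shows safety follow-up at days 30 and 70, patient follow-up at weeks 13, 26, 39 and 52 after last dosing, and a separate end-of-trial column.
- Section 4.8.1 ties completion of the whole trial to the last patient's day-70 visit. That equates the two dates for that patient only.
- The reporting-period rule in 10.2 lists the day-70 visit and the end-of-trial/withdrawal visit as alternatives, so the protocol itself treats them as distinct.
- The largest scheduled gap is 52 × 7 − 70 = 294 days. This is an upper bound: under 8.2, escalation patients who start other anti-cancer treatment leave the trial.

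**2. Which events are exposed?**

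| Event class | Affected by 10.2 versus 10.6? |
|---|---|
| SAEs, any grade or causality | No, excepted |
| Possibly related, non-serious, grade 3 or higher | No, excepted |
| Unrelated, non-serious, grade 3 or higher | Yes, if open at the safety follow-up visit |
| Non-serious, grade 1-2 | Yes, if open at the safety follow-up visit |

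The last row has clinical weight. Under 7.1, a possibly related AST, ALT or bilirubin rise of more than one grade from baseline (for example grade 0 to 2) that has not returned to grade 1 or lower within 7 days is a DLT, and a patient with a DLT stops trial drug at once. If non-serious, that is an AESI close to the last dose, already known not to resolve quickly, and outside the exception.

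**3. Does the SAP neutralise the difference?** No. Section 17.3 censors subjects without an event in the Kaplan-Meier curves for time to first AESI. For resolution it gives no common cut-off and no handling of unresolved events.

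**4. Illustration of size.** All inputs except days 70 and 364 are assumptions: onset on the last dosing day and exponential time to resolution with median m, so λ = ln 2 / m.
- Share resolved by day T: 1 − exp(−λT).
- Mean time among events resolved by T: 1/λ − T·exp(−λT) / (1 − exp(−λT)).

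| Assumed median | Resolved by day 70 | Resolved by day 364 | Mean time if resolved, cut at 70 | Mean time if resolved, cut at 364 |
|---|---|---|---|---|
| 14 days | 96.9% | 100.0% | 17.9 d | 20.2 d |
| 30 days | 80.2% | 100.0% | 26.0 d | 43.2 d |
| 60 days | 55.5% | 98.5% | 30.3 d | 81.0 d |

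For m = 60: 1 − 0.5^(70/60) = 55.5% and 1 − 0.5^(364/60) = 98.5%. The day-364 columns are a ceiling, for a patient followed to week 52 under 10.2. Onset well before the last dose narrows the gap. Onset 35 days after the last dose widens it: 82.3%, 55.5% and 33.3% resolved by day 70 for the three medians.

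**The case against.** The case against giving this much weight is substantial, and most of it stands as a limit on the point.

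- **Severe toxicity.** A reader might infer that reversibility of serious or severe related hepatotoxicity and diarrhea is at risk. The exception in both sections rules that out. It is worded for events open after end of trial, so 10.6 alone is silent on the interval between the safety follow-up visit and end of trial. Table 1-1 footnote 18 continues AE collection for those classes during patient follow-up.
- **Day 30.** Because 8.3 lists two visits, a reader might infer that a site could close events at day 30. Section 10.2 ties the safety follow-up visit to day 70, as do 4.8.1 and 9.1.4. Day 70 is the natural reading; 10.6 simply fails to say so.
- **Section 10.2.6.** A reader might count this as a third competing rule with no end. It applies to laboratory AEs only, so it bears on the transaminase AESI and not on diarrhea as such. It can run alongside the general rule, and an adequate explanation also closes the event. What is missing is how it fits.
- **A full year of extra follow-up.** Footnote 18 limits AE collection in patient follow-up to essentially the excepted classes, and scheduled biochemistry ends at the day-70 visit. In practice this points sites towards 10.6 for lower-grade events. It does not cancel the instruction in 10.2, and 8.3 still sends follow-up data to the AE eCRF.
- **Early resolution is well observed.** Section 6.4.1 describes transaminase elevations as mainly a first-dose effect, and 7.2.2.1 has elevations of grade 2 or higher checked twice weekly for up to 4 weeks. Many events will therefore be seen to resolve under either rule.
- **Dose finding.** The MTD rests on DLTs within 28 days and is untouched.

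What survives is a direct conflict between two current instructions, for a defined class of events, feeding a planned table that has no common cut-off.

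**Conclusion.** The inconsistency is real and of limited reach. It concerns how long reported AEs are followed, and only for non-serious grade 1-2 events and unrelated non-serious events of grade 3 or higher still open at the safety follow-up visit. For those events, percentage resolved and time to resolution can vary with the rule a site follows. Restricting time to resolution to resolved events adds to this, because a shorter window drops the slow ones.

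The size cannot be computed: the documents give neither resolution times nor the number of events open at day 70. Under the assumptions above, the difference in share resolved is at most about 3 percentage points for a 14-day median (100.0 − 96.9 = 3.1) and 43 points for a 60-day median (98.5 − 55.5 = 43.0). Both are ceilings, within the affected class only and for that assumed onset. The point merits correction because the summaries describe the trial's main toxicities and the repair costs little. It does not call the dose-finding result into question.

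**What to change.** **Protocol.** Reconcile 10.2, 10.6 and 10.2.6 so that each event class has one stated end-point for follow-up, with the visit named by day. State how the laboratory rule relates to the general rule. Keep the existing exception. The choice of end-point is the sponsor's.

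**SAP 17.3.** Report AESI outcome as of one common cut-off for all subjects. For time to resolution, treat events unresolved at that cut-off as censored instead of dropping them, and censor earlier where AE follow-up ended earlier. List or summarise separately any later resolutions of the excepted events, so that the data the protocol deliberately collects past end of trial are not lost.

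**Cost.** Wording in three protocol sections and a short addition to the SAP. No new visits or data are needed. The SAP change helps even for data already collected, since it can be applied to recorded AE end dates and outcomes.

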10.7 Warnings and Precautions

No evidence available at the time of the approval of this trial protocol indicated that special warnings or precautions were appropriate, other than those noted in the provided investigator's brochure (IB). Additional safety information collected between IB updates will be communicated in the form of investigator notifications. This information will be included in the patient informed consent and should be discussed with the patient during the trial as needed.

10.8 Data Monitoring Committee

This trial will institute a data monitoring committee (DMC) which will function independently of all other individuals associated with the conduct of this clinical trial, including the site investigators participating in the trial. The DMC will consist at a minimum of two physicians with appropriate disease area qualifications and, where applicable, a statistician. The functions and responsibilities of the DMC will be described in the DMC Charter, which will be approved by the DMC.

During the dose escalation phase, the DMC will be responsible for reviewing safety and pharmacokinetic data after completion of the cohort on each dose-level. A DMC meeting including both an open and closed session will be held in order to discuss data. During the open session, sponsor employees and investigators will participate together with the DMC. During the closed session, only DMC members will participate. After the closed session, the sponsor will be informed of the DMC's recommendations. The sponsor safety committee will hereafter meet to evaluate the recommendations provided by the DMC and decide whether the dose of IMP should be escalated, de-escalated or held at same dose-level.

During the expansion phase of the trial, the DMC may meet at regular intervals, as defined in the DMC charter.

The DMC will also review the safety, pharmacokinetic and efficacy data at the end of the trial in order to provide an overall Risk Benefit assessment, as defined in the DMC charter.

11 STATISTICS

All statistical analyses will be performed by a Contract Research Organization (CRO), under the direction of sponsor personnel.

The Statistical Analysis Plan (SAP) will be developed and finalized before database lock and will describe the patient populations to be included in the analyses, and procedures for accounting for missing, unused, and spurious data. This section is a summary of the planned statistical analyses of the primary and secondary endpoints.

All presentations will be done separately for the dose escalation part and the expansion part.

In the reporting of the dose escalation part tables will report by cohort while in the expansion part tables will report by indication.

All data will be listed. Baseline is defined as the latest available measurement made before the first treatment with IMP.

A patient will be considered as having completed the trial when all planned trial visits have been performed.

